6.5. Dose Delays and Modification

Dose modification of 16 mg/kg Dara-IV or 1800 mg Dara-SC (increase or decrease) is not permitted. Dose delay is the primary method for managing daratumumab-related toxicities. On the first day of each new treatment cycle and before each dose of study drug, the subject will be evaluated by the treating physician for possible toxicities that may have occurred after the previous dose(s). Toxicities are to be assessed according to NCI-CTCAE, Version 4.03. Cycle delays will be based on the toxicity experienced during the previous cycle of therapy or newly encountered on Day 1 of a cycle.

The study treatment must be held if any of the following criteria are met, to allow for recovery from toxicity, regardless of relationship to study drug:

- Grade 4 hematologic toxicity, except for Grade 4 lymphopenia
- Grade 3 or higher thrombocytopenia with bleeding
- Febrile neutropenia
- Neutropenia with infection, of any grade
- Grade 3 or higher non-hematologic toxicities with the following exceptions:
 - Grade 3 nausea that responds to antiemetic treatment within 7 days
 - Grade 3 vomiting that responds to antiemetic treatment within 7 days
 - Grade 3 diarrhea that responds to antidiarrheal treatment within 7 days

- Grade 3 fatigue that was present at baseline or that lasts for <7 days after the last administration of daratumumab
- Grade 3 asthenia that was present at baseline or that lasts for <7 days after the last administration of daratumumab
- Grade 3 pain associated with symptoms of multiple myeloma (bone/joint pain)

Study treatment should be resumed when the toxicity has resolved to ≤Grade 2. If study drug administration does not commence within the prespecified window of the scheduled administration date (Table 4), then the dose will be considered a missed dose. Administration may resume at the next planned dosing date. A missed dose will not be made up.

Table 4: Daratumumab Administration Schedule

Cycles	Frequency	Dose Held	Dosing Restart
1 and 2	Weekly (q1wk)	>3 days	Next planned weekly dosing date
3 to 6	Every 2 weeks (q2wks)	>7 days	Next planned every 2 weeks dosing date
7+	Every 4 weeks (q4wks)	>14 days	Next planned every 4 weeks dosing date

Any dose hold of more than 28 days due to toxicity will result in permanent discontinuation of daratumumab. Dose holds of more than 28 days for other reasons should be discussed with the sponsor. If a dose delay occurs, then pharmacokinetic and pharmacodynamic assessments should be performed on (or relative to, in the case of C1D4 and C3D4 PK collections in the Dara-SC group) the actual day of study drug administration, not on the original scheduled administration day.

Delay of Day 1 drug dosing in any given cycle should not result in a skipped dose but should lead to a delay of the entire cycle instead. A minimum of 4 days between daratumumab doses must be observed.

A study drug dose held for more than 3 days from the per-protocol administration date for any reason other than toxicities suspected to be related to daratumumab should be brought to the attention of the sponsor at the earliest possible time. Subjects missing ≥3 consecutive planned doses of study drug for reasons other than toxicity should be withdrawn from treatment, unless, upon consultation with the sponsor and the review of safety and efficacy, continuation is agreed upon. Infusion-related reactions may occur upon re-initiation of daratumumab after a prolonged delay in treatment. Investigators should consider the applicable infusion reaction guidance provided in Section 6.4.2 when restarting treatment after a long delay.

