10. SUBJECT DISCONTINUATION OF STUDY TREATMENT/ WITHDRAWAL FROM THE STUDY

10.1. Discontinuation of Study Treatment

Discontinuation of Study Treatment

If a subject's study treatment must be discontinued, this will not result in automatic withdrawal of the subject from the study. The End-of-Treatment Visits and Follow-up visit assessments should continue as specified in the Time and Events Schedule.

A subject's study treatment must be discontinued if:

- The investigator believes that for safety or tolerability reasons (eg, adverse event) it is in the best interest of the subject to discontinue study treatment.
- The subject becomes pregnant unless the subject (or the subject's legally acceptable representative), investigator, and sponsor agree the benefits outweigh the risks to the fetus and continuation of study treatment is in the best interests of the subject
- The subject (or the subject's legally acceptable representative) withdraws consent for administration of study drug
- The subject experiences unacceptable toxicity, including IRRs described in Section 6.4, Management of Injection-site and Infusion-related Reactions
- The subject's dose is held for more than 28 days, or if 3 consecutive planned doses of daratumumab are missed for reasons other than toxicity unless, upon consultation with the sponsor and the review of safety and efficacy, continuation is agreed upon
- The subject experiences disease progression (please see below); relapse from CR is not considered as disease progression
- The subject experiences a second primary malignancy that cannot be treated by surgery alone (however, a subject who develops a malignancy that can be cured surgically may continue to receive the assigned study treatment and should continue to be followed for subsequent progression of multiple myeloma)

The primary reason for discontinuation of study treatment will be recorded in the eCRF.

Study treatment will continue until confirmation of PD. Before subjects are discontinued from study treatment because of suspected PD:

1. The investigator (or designee) will provide documentation of disease progression (for example, by completing a disease progression form or by contacting the IWRS) as soon as possible and within 48 hours of confirmation of disease progression.

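### From Cycle 7, Protocol 6.5 tells sites both to skip and not to skip a Day 1 dose that is more than 14 days late, and the 28-day stopping rule in 6.5 is not matched by Section 10.1

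*Protocol*

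**What the plan says.** Protocol 6.5 states the general rule first. If study drug is not started within the Table 4 window, "then the dose will be considered a missed dose", and "A missed dose will not be made up". Table 4 sets the limit at more than 3 days in Cycles 1-2, more than 7 in Cycles 3-6 and more than 14 from Cycle 7. For Cycles 7+ the restart entry reads "Next planned every 4 weeks dosing date". Day 1 doses are not excepted.

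Below Table 4 the same section says "Delay of Day 1 drug dosing in any given cycle should not result in a skipped dose"; all of that cycle is to be pushed back instead. Neither passage is given precedence.

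On stopping, 6.5 says "Any dose hold of more than 28 days due to toxicity will result in permanent discontinuation of daratumumab". For holds of that length with any other cause it asks only that they be taken up with the sponsor. Section 10.1 lists, among the conditions under which treatment must be discontinued, that the subject's "dose is held for more than 28 days, or if 3 consecutive planned doses of daratumumab are missed for reasons other than toxicity". That bullet ends with an exception where continuation is agreed after consulting the sponsor.

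**The concern.** These are the instructions by which sites pause, restart and stop study drug for toxicity. From Cycle 7 each cycle has a single dose, on Day 1, so the Cycles 7+ row of Table 4 can only ever apply to a Day 1 dose. What it prescribes is what the Day 1 sentence rules out. Two sites that both follow the protocol can give the same patient a different exposure.

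The skip route also ends on the edge of the 28-day limit, and 6.5 and 10.1 do not state that limit in the same way, so whether treatment may continue can depend on which section is read.

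The SAP reports what results: cycle delays, dose delays, dose skips and relative dose intensity (SAP 4.7), discontinuations due to adverse events (6.1.6) and treatment modifications (6.1.7). SAP 2.3 names delay or skip as the main way of managing toxicity; Protocol 6.5 names delay only.

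**Working it through.** No sample size, power or alpha is involved. The check is a count of days.

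**Inputs**
- Cycle length 28 days; one dose per cycle from Cycle 7; doses on Days 1 and 15 in Cycle 6 (Protocol 6.2, Table 3).
- Missed-dose limit from Cycle 7: held more than 14 days (Table 4).
- Day 1 visit window from Cycle 4: ±3 days (Table 3, and the note heading Table 1).
- Treatment resumes once toxicity is Grade 2 or lower (6.5).
- Stop: toxicity hold strictly longer than 28 days (6.5).
- Assumption: days are counted from the scheduled Day 1, taken as day 0. Section 6.5 gives an origin only for a different rule, the sponsor notification of holds over 3 days, which it counts from the per-protocol date.

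**Step 1. Where the two rules part (Cycle 7 onward)**

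| Recovery | Table 4 rule | Day 1 rule |
|---|---|---|
| Up to day 14 | Late dose given | Late dose given |
| Days 15-28 | Dose missed; restart at day 28 (±3) | Dose given on recovery; cycle shifted |

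For recovery on days 25-28 the calendar date of the next dose can coincide, because the window opens on day 28 − 3 = 25. One rule still records a missed dose and the other a delayed cycle.

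**Step 2. Size, for recovery on day 15**
- Cycle 8 onward, previous dose 28 days before the scheduled date: shift 28 + 15 = 43 days; skip 28 + 28 = 56 days.
- Cycle 7 itself, previous dose on Cycle 6 Day 15, 14 days before: shift 14 + 15 = 29 days; skip 14 + 28 = 42 days.
- The difference is 13 days in either case.

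**Step 3. The 28-day limit**
- Skip route at the nominal date: hold = 28 days. This is not more than 28, so the stop is not triggered.
- Window 28 ± 3 = days 25-31. Days 25-28 are within the limit; days 29, 30 and 31 exceed it. So 3 of the 7 permitted restart days cross the limit, if the whole interval counts as a toxicity hold.

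**Step 4. Earlier cycles**
- Applied literally to Day 1, Table 4 restarts on day 7 in Cycles 1-2 and day 14 in Cycles 3-6. With the visit windows (±1 and ±3 days) the latest restarts are 7 + 1 = 8 and 14 + 3 = 17. The 28-day limit is not approached.
- In these cycles Table 4 can be read as covering only the doses after Day 1 (Days 8, 15, 22). That reading removes the conflict, but the text does not state it.

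**Step 5. Section 10.1 against 6.5.** The bullet can be read in three ways:
- The non-toxicity qualifier and the sponsor exception both attach only to the three missed doses. Then any hold over 28 days, including one not due to toxicity, is a mandatory stop; 6.5 asks only for discussion of the latter.
- The exception attaches to both limbs and the qualifier only to the missed doses. Then a toxicity hold over 28 days can be continued by agreement; 6.5 has no such exception.
- The qualifier attaches to both limbs. Then the 28-day toxicity stop does not appear in the bullet. The separate entry on unacceptable toxicity gives no day limit.

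None of the three reproduces 6.5.

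**The case against.** The best defence is that the Day 1 sentence is the more specific rule and operates as an exception to Table 4. Other text points that way: 6.5 bases cycle delays on toxicity in the previous cycle or on Day 1, and the note heading Table 1 has later Day 1 dates adjusted to keep the 28-day cycle. This succeeds for Cycles 1-6. It fails from Cycle 7, because the Cycles 7+ row would then have nothing to apply to. Reading the next planned date as a re-planned one does not help either, since the dose is still classed as missed.

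A reader might infer that a patient who recovered on day 15 would be permanently discontinued under the skip rule. The documents do not support that. The skip route ends at exactly 28 days, and the automatic stop is for holds due to toxicity. After recovery the remaining wait is arguably scheduling, which 6.5 refers to discussion with the sponsor. Discontinuation follows only if the count continues after recovery and the restart falls 1-3 days late. What stands is that 6.5 does not settle how the count works.

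A reader might also infer that the rules clash for every late Day 1 dose. They do not: from Cycle 7 a delay of 14 days or less is handled the same way by both.

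On 10.1, the exception does sit directly after the missed-dose condition and echoes the wording of 6.5 for that condition, which favours the first reading in Step 5. On that reading the toxicity stop is intact, but the mismatch for non-toxicity holds remains.

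Finally, the strict conflict begins after Cycle 3 Day 1, when the trough co-primary is measured; ORR is analysed by intention to treat with a treatment-policy strategy for discontinuation; both arms follow the same rules; and the documents give no frequency of such long holds. These points are sound and limit the consequence. They do not resolve the contradiction.

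**Conclusion.** The point holds within limits. For Day 1 doses more than 14 days late from Cycle 7, Protocol 6.5 contradicts itself. For recovery on day 15 the difference is 13 days between doses: 43 against 56 from Cycle 8, and 29 against 42 for Cycle 7. In Cycles 1-6 the two passages can be reconciled by a reading that the protocol does not state. The skip route leaves no margin to the 28-day toxicity stop, the permitted window reaches days 29-31, and neither the start of the count nor the status of the wait after recovery is defined. Section 10.1 does not match 6.5 on any of its readings.

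The day counts assume that a hold runs from the scheduled date. How many patients are affected cannot be estimated from the documents. The effect is on patient management and on reported delays, skips, dose intensity and discontinuations. A reader might extend this to the non-inferiority conclusions on ORR or trough concentration; nothing in the documents shows that they are affected.

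**What to change.** Reconcile Protocol 6.5 (the text before and after Table 4), Tables 3 and 4, and the 10.1 bullet in one rule set that:

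1. states whether Table 4 applies to Day 1 doses and, accordingly, what the Cycles 7+ row governs;
2. states the date from which the 28 days run, whether time after recovery counts, and how the count relates to the Day 1 visit window;
3. uses the same wording for holds over 28 days in 6.5 and 10.1, including whether the sponsor-agreement exception reaches toxicity holds.

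SAP 2.3 should then describe delay and skip in the same terms. Which rule is right is for the sponsor to decide. The cost is amendment wording and a letter to sites, with no added visits or procedures.

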7. TREATMENT COMPLIANCE

Study drug (Dara-IV or Dara-SC) will be administered by qualified site staff, and the details of each administration will be recorded in the electronic case report form (eCRF). Additional details are provided in the IPPI.

8. PRESTUDY AND CONCOMITANT THERAPY

All prestudy antineoplastic and multiple myeloma therapies must be recorded at screening. Throughout the study, investigators may prescribe any concomitant medications or treatments deemed necessary to provide adequate supportive care except for those listed in Section 8.3, Prohibited Therapies. The sponsor must be notified in advance (or as soon as possible thereafter) of any instances in which prohibited therapies are administered.

Routine systemic use of the following concomitant medications will be collected in the eCRF and recorded in the source documents beginning with signing of the ICF to 30 days after the last dose of the last study treatment during the data collection period or until the start of subsequent anticancer treatment, if earlier: growth factors, transfusions, anti-infectives (antibacterials, antivirals, and antimycotics), steroids, anti-arrhythmics and other cardiac supportive therapy, anti-epileptics, centrally acting psychiatric medication, anti-histamines and other medications targeting postinfusion systemic reactions, bisphosphonates, and any anticancer therapy (including radiation). Concomitant medications to manage adverse events and serious adverse events will be recorded as per Section 12.3, Procedures.

8.1. Recommended Therapies

8.1.1. Bisphosphonate Therapy

Bisphosphonate therapy is strongly recommended for all subjects with evidence of lytic destruction of bone or with osteopenia. Bisphosphonate therapy is recommended to be continued per treatment guidelines (NCCN 2013¹⁷; Moreau 2013¹⁶). Commercially available IV bisphosphonates (pamidronate and zoledronic acid) are preferred when available, and should be used according to the manufacturer's recommendations, as described in the prescribing information, for subjects with osteolytic or osteopenic myelomatous bone disease. Oral bisphosphonates may be used as alternatives if IV bisphosphonates are not available at the study site. Investigators should use the same route of bisphosphonate therapy for all subjects at their sites.

8.1.2. Therapy for Tumor Lysis Syndrome

Subjects should be monitored for symptoms of tumor lysis syndrome. Management of tumor lysis syndrome, including hydration for abnormal laboratory test results such as hyperkalemia, hyperuricemia, and hypocalcemia, is highly recommended. High-risk subjects (ie, those with a high tumor burden) should be treated prophylactically in accordance with local standards (eg, rehydration, diuretics, allopurinol 300 mg daily, and medication to increase urate excretion).

8.1.3. Therapy for *Pneumocystis carinii/jirovecii*

Pneumocystis carinii/jirovecii pneumonia prophylaxis should be considered, as per institutional guidelines.

8.1.4. Prophylaxis for Herpes Zoster Reactivation

The initiation of antiviral prophylaxis to prevent herpes zoster reactivation within 1 week after starting study treatment and continuing for 3 months following study treatment is recommended. Acceptable antiviral therapy includes acyclovir (eg, 400 mg given orally 3 times a day, or 800 mg given orally 2 times a day or per institutional standards), famcyclovir (eg, 125 mg given orally, twice a day or per institutional standards), or valacyclovir (eg, 500 mg given orally, twice a day or per institutional standards), initiated within 1 week after the start of study drug.

8.1.5. Prevention of Steroid Induced Gastritis

Dexamethasone and other steroids may induce gastritis. Medications to prevent gastritis are permitted per institutional guidelines, for example proton pump inhibitors (omeprazole or equivalent), sucralfate, or H2 blockers (ranitidine or equivalent).

8.1.6. Management of Hepatitis B Virus Reactivation

Primary antiviral prophylaxis is permitted as per local standard of care. Per protocol, HBV DNA testing by PCR is mandatory for subjects at risk for HBV reactivation, see Section 9.7.

For subjects with evidence of positive HBV serology, monitor for clinical and laboratory signs of HBV reactivation during, and for at least 6 months following the end of study treatment. Manage subjects according to current clinical guidelines. Consider consulting a hepatitis disease expert as clinically indicated.

For subjects who develop reactivation of HBV while on study treatment, suspend study treatment and institute appropriate treatment for HBV or follow country-specific clinical guidelines. Resumption of study treatment in subjects whose HBV reactivation is adequately controlled should be discussed with physicians with expertise in managing HBV.

8.2. Permitted Therapies

Subjects are to receive full supportive care during the study. The following medications and supportive therapies are examples of support therapies that may be used during the study:

- Antivirals
- Colony stimulating factors, erythropoietin, and transfusion of platelets and red cells is allowed, except as prophylaxis during Cycle 1
- Laxatives or stool softeners
- Adequate hydration is recommended for prevention of myeloma-related kidney disease.

Other symptoms may be managed according to institutional guidelines provided prohibited therapies are not administered (see Section 8.3, Prohibited Therapies).

8.3. Prohibited Therapies

The sponsor must be notified in advance (or as soon as possible thereafter) of any instances in which prohibited therapies are administered. Concomitant administration of any other antineoplastic therapy for the intention of treating multiple myeloma is prohibited, including medications that target CD38, as well as medications used for other indications that have anti-myeloma properties (eg, interferon and clarithromycin). Continuation of study treatment (during or after emergency orthopedic surgery or radiotherapy because of subject benefit) may only occur in the absence of disease progression and after consultation with and approval by the sponsor.

Emergency radiotherapy may consist of localized radiotherapy for pain control or for stabilization of an extensive bone lesion at high risk of pathologic fracture or damage to surrounding tissues in a subject for whom delay of systemic therapy is not appropriate. Radiotherapy must occur within the first 2 cycles of treatment and only if disease progression has not occurred. Before radiotherapy, the sponsor will review the evidence and confirm that disease progression has not occurred.

Concomitant administration of investigational agents and of commercially available agents with activity against or under investigation for multiple myeloma are prohibited. Systemic corticosteroids (>10 mg prednisone per day or equivalent) (other than those given for IRRs as described in Section 6.3, Predose and Postdose Medications) should be avoided. Nonsteroidal anti-inflammatory agents should be avoided to prevent myeloma-related kidney disease.

9. STUDY EVALUATIONS

9.1. Study Procedures

9.1.1. Overview

The Time and Events Schedules (Table 1 and Table 2) summarize the frequency and timing of measurements applicable to this study. Every effort should be made to keep subjects on the planned study schedule including subjects who switch from Dara-IV to Dara-SC following Protocol Amendment 4. At each visit, study assessments should be completed before study treatment administration. The modified-CTSQ should be conducted and completed before any tests, procedures, or other consultations for that visit, to prevent influencing subject perceptions.

Disease evaluations must be performed every 28 days (± 7 days) starting from Cycle 1 Day 1. Any missed visits, tests not performed, or examinations that are not conducted must be reported as such on the eCRF. Additional serum or urine pregnancy tests may be performed, as determined necessary by the investigator or required by local regulation, to establish the absence of pregnancy at any time during the subject's participation in the study.

The maximum blood volume for a subject who completes 8 cycles and the post-treatment assessments is approximately 490 mL. The total blood volume to be collected is estimated at approximately 34 mL for Screening, 100 mL for Cycles 1 and 2, 161 mL for Cycles 3-6, 21 mL at each subsequent cycle, 55-85 mL for pharmacokinetics (depending on treatment group), 5 mL

when CR is suspected or maintained, and 50 mL at the End-of-Treatment visit. This includes laboratory assessments associated with safety, efficacy, and pharmacokinetic evaluations, as well as scientific research samples. Repeat or unscheduled samples may be taken for safety reasons or for technical issues with the samples. In the Follow-up Phase, subjects who discontinue study drug prior to PD will continue to have approximately 20 mL blood drawn every 2 months for serum disease evaluations.

Subjects benefiting from daratumumab after the data collection period has ended may continue receiving study drug (see [Attachment 13](#)).

9.1.2. Screening Phase

The Screening Phase begins when the ICF is signed. During the Screening Phase, eligibility criteria will be reviewed and a complete clinical evaluation will be performed as specified in the Time and Events Schedule. Screening procedures will be performed within 28 days before randomization, with the exceptions of disease evaluations, laboratory tests, and pregnancy tests. Serum and urine baseline disease evaluations are to be performed by the central laboratory within 14 days before randomization. It is not mandatory to collect these samples again at the Cycle 1, Day 1 visit. Results from skeletal survey and radiologic plasmacytoma assessments performed as routine follow up for subject's disease within 42 days before randomization and bone marrow aspirate/biopsy within a maximum of 42 days before randomization may be used without these tests being repeated. If the 24h collection of urine M-protein quantitation by electrophoresis (UPEP) began before informed consent was obtained as part of routine patient care, the sample can be used in this study as long as it was sent to the central lab for analysis after the informed consent was obtained. During Screening, a pregnancy test must be performed within 14 days prior to dosing. If approved by the sponsor, subjects who are screen failures may be rescreened if their condition changes (see Section 4.2, Exclusion Criteria, for details).

Prior to randomization, the sponsor will review key eligibility criteria for all subjects. Eligibility information will be provided to the sponsor for review prior to approval for randomization being granted by the sponsor. If the sponsor agrees that the eligibility criteria have been met, then the investigator will receive confirmation that the subject may be randomized into the study. If the sponsor considers that the eligibility criteria have not been met, then the sponsor will contact the investigator to discuss the subject.

